 Plasma samples for pharmacokinetic assessment will be taken at baseline (prior to dosing on Day 15) and at 4 hours (±2 hours), 12 hours (±2 hours) after dosing on Day 15, and at 24 hours (±2 hours) after dosing on Day 15 (prior to dosing on Day 16). (Day 15 only)

8.6 Day 22 ± 3 days (these assessments will also be done at Early Termination or Discontinuation from the study)

The following assessments will be performed on Day 22 (\pm 3 days):

- 1. Vital Signs (temperature/pulse/supine blood pressure)
- 2. SpO₂
- 3. Physical examination (including weight)
- 4. 12-lead ECG (single)
- 5. Chest X-ray or CT scan
- 6. Clinical Laboratory tests
 - a. Hematology (Appendix A)
 - b. Serum chemistry (Appendix A)
 - c. Urinalysis
- 7. Adverse events
- 8. Record the usage of any concomitant medications and ongoing treatments.
- 9. Assessment of primary and secondary endpoints

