# 6.12.1 Primary Endpoint

QMD Ref: Worldwide-TMP-ST-005-7.0 Effective: 12Aug2019 Governing QMD: Worldwide-SOP-ST-		
Confidentiality Statement		
This document is the property of Worldwide Clinical Trials Inc. and may not be duplicated, copied, altered or removed from company without prior approval from Worldwide Quality Assurance or in compliance with Worldwide Standard Operating Procedures.		

REF: Worldwide-TMP-QA-001f-1.3

Worldwide Clinical Trials Controlled Quality Management Document		
WORLDWIDE CLINICAL TRIALS	Sponsor:	Veru Inc.
	Protocol Number:	V0211901
STATISTICAL ANALYSIS PLAN. PHASE 2-3-4		

The primary endpoint for the study is the proportion of subjects that are alive without respiratory failure at Day 29. Respiratory failure is defined as endotracheal intubation and mechanical ventilation, extracorporeal membrane oxygenation, high-flow nasal cannula oxygen delivery, noninvasive positive pressure ventilation, clinical diagnosis of respiratory failure with initiation of none of these measures only when clinical decision making is driven solely by resource limitation.

This analysis will compare the percentage of subjects that are alive without respiratory failure on Day 29 (responder).

Responders are subjects who have Grade 0-4 on the WHO Ordinal Scale for Clinical Improvement on Day 29. If subject was discharged from the hospital prior to Day 29 and WHO Ordinal Scale for Clinical Improvement is not collected at Day 29 then the last available observation before or at the time of discharge will be carried forward.

Non-responders are subjects who died before Day 29 or has Grade 5, 6, 7, or 8 on the WHO Ordinal Scale for Clinical Improvement on Day 29.

The number and percentage of responders will be summarized by treatment group. Responders will be analyzed using a logistic regression model. This model will include treatment as a factor, and study site, remdesivir use (No/Yes), dexamethasone use (No/Yes) and WHO Ordinal Scale for Clinical Improvement at baseline as a covariates. Odds ratios, standard errors, 95% confidence intervals and p-values for the treatment difference will be presented.

The primary analysis will be performed on the ITT population. A sensitivity analysis will be performed repeating the analysis on the EE population.

Example SAS code for the analysis is as follows:

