#### **6.12.2** Secondary Endpoints

# 6.12.2.1 Change in mean WHO Ordinal Scale for Clinical Improvement at Day 15, Day 22 and Day 29

The mean change in WHO Ordinal Scale for Clinical Improvement from baseline to Day 15, Day 22 and Day 29 will be assessed.

Baseline for WHO Ordinal Scale is the last available record up to and including Day 1. If subject died or was discharged from the hospital prior to Day 15, 22 or 29 and WHO Ordinal Scale for Clinical Improvement is not collected or record is otherwise missing at those timepoints then the last available observation before or at the time of death/discharge will be carried forward.

Analysis will be performed using two different approaches, including the LOCF values and excluding LOCF values. Further, these analyses will be repeated using separate baseline definition. As the time of WHO Ordinal Scale is collected it cannot be definitely confirmed if Day 1 record was taken before or after start of study treatment. Sensitivity analysis will be performed using the WHO Ordinal Scale from Screening record.

Descriptive statistics (n, mean, standard deviation, median, minimum and maximum) will be summarized for absolute values and change from baseline by treatment group and visit.

Change from baseline will be analyzed using mixed model for repeated measures (MMRM) including treatment, visit and treatment-by-visit interaction as fixed effects, and study site, remdesivir use (No/Yes), dexamethasone use (No/Yes) and WHO Ordinal Scale for Clinical Improvement at baseline as covariates. The resulting F-tests will be based on Kenward-Roger's adjusted degrees of freedom. Subject effect will be assumed to be random and an unstructured covariance structure will be used for within subject variation. If this model does not converge then the following covariance matrices will be used in order until the model converges: Toeplitz, first-order autoregressive, and compound symmetry. Least squares means, standard errors, 95% confidence intervals and p-values for treatments and treatment differences at each visit (study days 15, 22, 29, 45 and 60) will be presented.

QMD Ref: Worldwide-TMP-ST-005-7.0 Effective: 12Aug2019 Governing QMD: Worldwide-SOP-ST-0		
Confidentiality Statement		
This document is the property of Worldwide Clinical Trials Inc. and may not be duplicated, copied, altered or removed from company without		

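### When a discharged subject misses the analysis visit, the SAP carries forward the WHO score from discharge and, read literally, skips any scheduled score observed in between

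*SAP*

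**What the plan says.** SAP 6.12.1 defines the primary endpoint from the WHO ordinal scale: "Responders are subjects who have Grade 0-4 on the WHO Ordinal Scale for Clinical Improvement on Day 29", and "Non-responders are subjects who died before Day 29 or has Grade 5, 6, 7, or 8" on that day. The carry-forward has a two-part trigger, discharge before Day 29 and no score at that visit: if the score is "not collected at Day 29 then the last available observation before or at the time of discharge will be carried forward". SAP 6.12.2.6 repeats the primary analysis at Days 15 and 22.

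SAP 6.12.2.1 (change in WHO score at Days 15, 22 and 29) has a similar rule: when the visit score is missing, "then the last available observation before or at the time of death/discharge will be carried forward". It calls these LOCF values and plans the analysis both with and without them.

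The protocol expects scores after discharge. Dosing stops at discharge or after 21 days (Appendix B). Sections 8.5 (Day 15), 8.6 (Day 22) and 8.7 (Day 29) each list "Assessment of primary and secondary endpoints", and none exempts discharged subjects.

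**The concern.** The rule looks backwards from the discharge date, not from the missing visit. A subject discharged on Day 8 may be scored at Day 15 and Day 22 and then miss Day 29. Read literally, the Day 29 value is the Day 8 score, and the two later observations are ignored.

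For the primary endpoint, a subject last seen in respiratory failure could be counted as alive without it. For WHO change, a subject scored 4 at discharge and 1 at Day 22 would return to 4 at Day 29, although the only later evidence is a 1. Two programmers could also differ: one following the sentence, the other following the LOCF label.

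**Working it through.** The documents state no figure on this point, so there is nothing to reproduce. The check applies the rule to possible records and then sizes one reclassification.

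**Step 1. Apply the rule.** Inputs: the SAP 6.12.1 trigger, carried score and responder cut, and the Day 22 visit in Protocol 8.6. The comparison rule uses the last score on or before Day 29, including scores after discharge.

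| Discharge score | Day 22 | Day 29 | SAP rule, literal | Last score on or before Day 29 |
|---|---|---|---|---|
| 3 | 5 | missing | 3, responder | 5, non-responder |
| 3 | 5 | 5 collected | non-responder | non-responder |
| 3 | 6 | died before Day 29 | non-responder | non-responder |
| 4 | 1 | missing | 4, responder | 1, responder |
| 5 | 2 | missing | 5, non-responder | 2, responder |
| 5 | 2 | 2 collected | responder | responder |

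Two of the six paths change. Both need a missing Day 29 score, an interim post-discharge score, no known death before Day 29, and scores on opposite sides of the 4/5 cut.

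**Step 2. Which visits are exposed.** On the Appendix B schedule, the Day 22 analysis can skip a Day 15 score, and the Day 29 analysis can skip Day 15 or Day 22. No post-baseline endpoint visit is scheduled before Day 15. Scores at Days 45 and 60 come after the endpoint and do not bear on it.

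**Step 3. Size of one reclassification.** With 20 per arm (SAP 5), one subject is 1/20 = 5 percentage points. The counts below are assumed, because the documents give no rates. The test is the pooled-variance z-test in the SAP's responder-rate sensitivity code, z = (p1 − p2) / √[p(1 − p) × 2/20], with Barnard's test beside it. It is not the primary logistic regression.

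- 18/20 vs 12/20: p = 30/40 = 0.750; z = 0.30/0.137 = 2.19; P = 0.029 (Barnard 0.039).
- One treated responder reclassified, 17/20 vs 12/20: p = 29/40 = 0.725; z = 0.25/0.141 = 1.77; P = 0.077 (Barnard 0.107).
- One placebo non-responder reclassified, 18/20 vs 13/20: p = 31/40 = 0.775; z = 0.25/0.132 = 1.89; P = 0.058 (Barnard 0.081).

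**Step 4. How often, under assumptions only.** Suppose 70-90% are discharged before Day 29, 10-20% of these miss the Day 29 score, and 5-10% of those have an observed relapse at an interim visit. Expected relapses scored as responses per arm:

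- low: 20 × 0.70 × 0.10 × 0.05 = 0.07
- high: 20 × 0.90 × 0.20 × 0.10 = 0.36

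This treats relapse and a missing Day 29 score as independent.

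**Step 5. WHO change.** If every discharged subject missing Day 29 had an interim score 2 points below the discharge score, the arm mean at Day 29 would be too high by 0.70 × 0.10 × 2 = 0.14 to 0.90 × 0.20 × 2 = 0.36 points. Multiply by the share who actually have such a score, which is unknown.

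**Step 6. Would another analysis show it?** The primary sensitivity analyses in 6.12.1 are a repeat on the EE population and the responder-rate differences. Both use the same derived response. Protocol 9.3.1 would have excluded subjects whose Day 29 status could not be established, and counted them as non-responders in a sensitivity analysis. The SAP has neither, and SAP 9 does not list the change. The WHO listing (16.2.6.2) would show the individual record, but no primary analysis would.

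**The case against.** The affected group is small. A subject who relapses to 5-7 by Day 22 will usually be an inpatient. If still in hospital at Day 29, a score is easy to obtain. If the subject has died, the outcome is non-response. If discharged a second time, the rule can be read as meaning the later discharge, which brings the readmission scores into scope. Relapse and a missing Day 29 score are therefore unlikely to be independent, and 0.07 to 0.36 is more likely too high than too low. Protocol 8.10 also regards discharge as completing the efficacy portion, so interim scores may be few. All of this stands, and it is why the point is narrow.

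It can also be said that the LOCF label in 6.12.2.1 shows the ordinary meaning was intended. That is plausible, but the sentence says otherwise. The exploratory AUC in 6.12.3.1 uses all available measurements up to Day 15 before carrying forward, with no cut-off at discharge. The same scale is thus handled in two ways.

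Some stronger readings are tempting but not supported:

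- *The rule overrides any later score.* It does not. A score collected at Day 29 is always used.
- *Recovered subjects lose their response.* A move from 3 or 4 to 0-2 is a response either way. Only a discharge score of 5 or more is affected.
- *The carried score is always an inpatient score, so WHO change is biased against the drug.* The AUC section's own example is a subject discharged as a 2, so the score may already be ambulatory. The documents do not settle a net direction. Secondary endpoints are descriptive (6.12.4), and the without-LOCF analysis is planned.

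**Conclusion.** The point holds in a narrow form. As written, 6.12.1, 6.12.2.6 and 6.12.2.1 pass over a scheduled score observed between discharge and the missing visit. In the primary endpoint this can turn a documented relapse to 5-7 into a response, or turn recovery after a discharge score of 5 or more into non-response. It does so only under the conditions in Step 1.

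It should be rare, and its frequency cannot be determined from the documents; the ranges in Steps 4 and 5 rest wholly on assumed rates. What is certain is the size per subject: 5 points in a 20-subject arm. In the assumed example, one subject is enough to cross 0.05. In WHO change with LOCF values, an observed improvement is replaced by the discharge score when that score is higher. The without-LOCF analysis exposes this only in part, because its contrast mixes the discharge anchor with the effect of carrying forward at all.

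This is an unpowered proof-of-concept study, and the point does not threaten the design. It is worth correcting because the stated rule gives a wrong result for identifiable records and the correction is cheap.

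**What to change.** For discharged subjects, replace the discharge anchor in SAP 6.12.1 and 6.12.2.1 with: *the last available scheduled score on or before the missing visit, including scores collected after discharge*. Through 6.12.2.6 the same rule then applies at Days 15 and 22. Leave death before the visit as non-response in the responder analyses.

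State separately whether scores from a readmission or an unscheduled assessment may be carried forward. SAP 6.2.9 disregards unscheduled post-baseline assessments, so using them needs an explicit exception there.

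Cost: a sentence in two sections, one statement on 6.2.9, and a small programming change. No new data are needed.

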# **6.12 Efficacy Analyses**

All statistical tests will be performed using a two-tailed 5% overall significance level, unless otherwise stated. All comparisons between treatments will be reported with 95% confidence intervals for the difference.

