Responder rates and differences between treatment groups in responder rates will be calculated as sensitivity analysis for primary endpoint. Wald method will be used for 95% confidence intervals and testing of treatment differences.

QMD Ref: Worldwide-TMP-ST-005-7.0 Effective: 12Aug2019	Governing QMD: Worldwide-SOP-ST-001	
Confidentiality Statement		
This document is the property of Worldwide Clinical Trials Inc. and may not be duplicated, copied, altered or removed from company without		
prior approval from Worldwide Quality Assurance or in compliance with Worldwide Standard Operating Procedures.		

REF: Worldwide-TMP-QA-001f-1.3

Worldwide Clinical Trials Controlled Quality Management Document		
WORLDWIDE CLINICAL TRIALS	Sponsor:	Veru Inc.
	Protocol Number:	V0211901
STATISTICAL ANALYSIS PLAN, PHASE 2-3-4		

Example SAS code for the analysis is as follows:

```
proc freq data=XXX order=internal;
tables avisitn*trt01pn*avalc / riskdiff(column=2 equal var=null cl=wald);
exact riskdiff barnard(column=2);
ods output riskdiffcol2=riskdiff1 pdiffcls=waldci1 pdifftest=waldtest1
barnardstest=barnard1;
run;
```

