#### 6.12.2.4 Days on mechanical ventilation

Mechanical ventilation is defined as subject having 'Intubation and mechanical ventilation' or 'Ventilation + additional organ support – pressors, RRT, ECMO'.

'Days on mechanical ventilation' will be summarized using descriptive statistics (n, mean, standard deviation, median, minimum and maximum) by treatment group.

'Days on mechanical ventilation' will be the number of days on mechanical ventilation up to Day 29. If subject dies early in the study and was on mechanical ventilation at the time of the death then it is assumed that subject was on mechanical ventilation up to Day 29. A sensitivity analysis will be performed assigning the worst possible endpoint score for deaths (i.e., considered to be on mechanical ventilation from baseline up to Day 29 and setting days on mechanical ventilation to 29).

Treatment comparison will be based on analysis of covariance (ANCOVA) model including treatment as a factor, and study site, remdesivir use (No/Yes), dexamethasone use (No/Yes) and WHO Ordinal Scale for Clinical Improvement at baseline as covariates. Treatment difference, standard error, 95% confidence interval and p-value will be presented.

Example SAS codes for the analysis are as follows:

#### 6.12.2.5 All-cause mortality at Day 15, Day 22, and Day 29

The number and percentage for all-cause mortality will be summarized by treatment group and visit.

These endpoints will be analyzed using the same methodology as for the primary endpoint.

Responders are subjects who are alive at the time of the visit.

Non-responders are subjects who died before the visit.

Separate analysis will be performed for each visit.

QMD Ref: Worldwide-TMP-ST-005-7.0 Effective: 12Aug2019	Governing QMD: Worldwide-SOP-ST-001	
Confidentiality Statement		
This document is the property of Worldwide Clinical Trials Inc. and may not be duplicated, copied, altered or removed from company without		
prior approval from Worldwide Quality Assurance or in compliance with Worldwide Standard Operating Procedures		

Worldwide Clinical Trials Controlled Quality Management Document		
WORLDWIDE CLINICAL TRIALS	Sponsor:	Veru Inc.
	Protocol Number:	V0211901
STATISTICAL ANALYSIS PLAN. PHASE 2-3-4		

Responder rates and differences between treatment groups in responder rates will be calculated as sensitivity analysis using the same methodology as for the primary endpoint.

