# STATISTICAL ANALYSIS PLAN. PHASE 2-3-4

Table Number	Table Title	Included in Preliminary Analysis	Included in DSMB (Table No.)	Validation Method	Shell Number (if repeat)
14.1.5.3	Standard of Care (ITT Population)			IP	
14.2	Efficacy Data				
14.2.1	Primary Efficacy Endpoint				
14.2.1.1	Proportion of Subjects Alive and Free of Respiratory Failure by Visit (ITT Population)	Yes		IP	
14.2.1.2	Logistic Regression for Proportion of Subjects Alive and Free of Respiratory Failure by Visit (ITT Population)	Yes		Stat IP	
14.2.1.2a	Responder Rates for Proportion of Subjects Alive and Free of Respiratory Failure by Visit (ITT Population)			Stat IP	
14.2.1.3	Proportion of Subjects Alive and Free of Respiratory Failure by Visit (EE Population)			IP	14.2.1.1
14.2.1.4	Logistic Regression for Proportion of Subjects Alive and Free of Respiratory Failure by Visit (EE Population)			Stat IP	14.2.1.2
14.2.2- 14.2.11	Secondary Efficacy Endpoints				
14.2.2.1	Descriptive Statistics for WHO Ordinal Scale for Clinical Improvement by Visit - With LOCF values (ITT Population)	Yes		IP	
14.2.2.2	Mixed Model for Repeated Measures (MMRM) for Change from Baseline in WHO Ordinal Scale for Clinical Improvement - With LOCF values (ITT Population)	Yes		Stat IP	
14.2.2.3	Descriptive Statistics for WHO Ordinal Scale for Clinical Improvement by Visit - Without LOCF values (ITT Population)			IP	14.2.2.1
14.2.2.4	Mixed Model for Repeated Measures (MMRM) for Change from Baseline in WHO Ordinal Scale for Clinical Improvement - Without LOCF values (ITT Population)			Stat IP	14.2.2.2
14.2.2.5	Descriptive Statistics for WHO Ordinal Scale for Clinical Improvement by Visit - With LOCF values - Screening as Baseline (ITT Population)	Yes		IP	14.2.2.1
14.2.2.6	Mixed Model for Repeated Measures (MMRM) for Change from Baseline in WHO Ordinal Scale for Clinical Improvement - With LOCF values - Screening as Baseline (ITT Population)	Yes		Stat IP	14.2.2.2
14.2.2.7	Descriptive Statistics for WHO Ordinal Scale for Clinical Improvement by Visit - Without LOCF values - Screening as Baseline (ITT Population)			IP	14.2.2.1
14.2.2.8	Mixed Model for Repeated Measures (MMRM) for Change from Baseline in WHO Ordinal Scale for Clinical Improvement - Without LOCF values - Screening as Baseline (ITT Population)			Stat IP	14.2.2.2
14.2.2.9	Area Under Curve of WHO Ordinal Scale for Clinical Improvement (ITT Population)			IP	

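### With about 20 patients per arm, the Wald 95% interval specified for the responder-rate difference is usually 1 to 3 points short of its stated coverage and can disagree with the test coded beside it (minor)

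*SAP*

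**What the plan says.** SAP 6.12.1 makes logistic regression the primary analysis and adds responder rates and their difference as a sensitivity analysis. For that difference, "Wald method will be used for 95% confidence intervals and testing of treatment differences".

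The example code contains "tables avisitn*trt01pn*avalc / riskdiff(column=2 equal var=null cl=wald". This asks for Wald limits, but for a test of equality that uses the variance under the null hypothesis. A further statement, "exact riskdiff barnard(column=2", asks for exact limits and Barnard's test. The prose mentions neither and does not say which result is reported.

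For all-cause mortality, SAP 6.12.2.5 says that "differences between treatment groups in responder rates will be calculated as sensitivity analysis using the same methodology as for the primary endpoint". SAP 6.12 adds a general promise: "All comparisons between treatments will be reported with 95% confidence intervals for the difference". The output is Table 14.2.1.2a in SAP section 11, "Responder Rates for Proportion of Subjects Alive and Free of Respiratory Failure by Visit (ITT Population", with Table 14.2.5.2a as its mortality counterpart.

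SAP section 5 plans about 40 patients, 20 per arm. SAP section 4 says that no power calculation was done and that the study is proof-of-concept only.

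**The concern.** The Wald interval for a difference of two proportions is a large-sample method, and with 20 patients per arm it tends to be too narrow. An interval labelled 95% then claims more precision than it has.

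The interval and the coded test also use different variances. One table could therefore show an interval that excludes zero beside a non-significant p-value from the same procedure, and the text does not say which to rely on.

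What is at stake is how certain the difference looks. The point difference and the coded p-value are unaffected. The difference matters because the protocol summary frames the move to Phase 3 on a clinically relevant difference in proportions at Day 22, and this is the analysis that puts an interval on that scale.

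**Working it through.** The plan states no coverage figure, response rate or effect size, so there is no figure of its own to reproduce.

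**Inputs.** From the SAP: 20 per arm (section 5), two-sided 5% level and 95% intervals (6.12), Wald limits and null-variance test (6.12.1). Assumed: true response rates from 50% to 95% in 5-point steps, which gives 55 unordered pairs including equal rates.

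**Formulas.** With observed rates p1 and p2, d = p1 − p2, and pooled rate p:
- Wald limits: d ± 1.96 × √[p1(1−p1)/n1 + p2(1−p2)/n2]
- Coded test: z = d / √[p(1−p)(1/n1 + 1/n2)]
- Exact coverage: the sum, over all 21 × 21 = 441 tables, of the two binomial probabilities multiplied together, counting only tables whose limits contain the true difference.

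**Coverage at 20 v 20, 55 rate pairs.**

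| Limits | Below 95% | Below 94% | Median | Lowest | Highest |
|---|---|---|---|---|---|
| Wald | 53 | 46 | 93.5% | 85.8% | 98.8% |
| Miettinen-Nurminen | 29 | 2 | 95.0% | 93.6% | 98.8% |
| Newcombe | 23 | 1 | 95.2% | 94.0% | 99.8% |

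The Wald shortfall is 1 to 3 points in 42 of the 55 pairs; for example, coverage is 93.9% at 80% v 60% and 93.1% at 70% v 70%. The lowest value is at 95% v 90%. Coverage exceeds 95% only at 90% v 90% (96.0%) and 95% v 95% (98.8%).

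**No true difference, common rate 50% to 90%.** The Wald interval excludes zero in 4.0% to 8.1% of trials. The coded test rejects in 3.9% to 5.3%. The fault is therefore in the interval and not in the test.

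**Why interval and test part company.** With equal arms of n, the null variance exceeds the Wald variance by d²/(2n). The Wald interval can therefore exclude zero when the test does not reject, but never the reverse. Example, 18/20 v 13/20:
- d = 0.90 − 0.65 = 0.25
- Wald variance: 0.09/20 + 0.2275/20 = 0.015875, SE 0.1260, limits 0.25 ± 0.2470, or +0.3 to +49.7 points
- Null variance: p = 31/40 = 0.775; 0.775 × 0.225 × 0.1 = 0.0174375, SE 0.1321, z = 1.89, p-value 0.058
- The variances differ by 0.0015625 = 0.25²/40, as expected
- Barnard's p-value is 0.081; Miettinen-Nurminen limits are −1.3 to +49.3, Newcombe −1.3 to +47.9

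**How often.** At 20 v 20 the Wald interval excludes zero while the coded test has p>0.05 in 14 of 441 tables (seven and their mirror images). At true rates of 90% v 70% these tables arise in 4.7% of trials. Miettinen-Nurminen limits conflict with the coded test in none of the 441. Newcombe limits conflict in 4, all with the test rejecting and the interval including zero.

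**Unequal arms.** At 19 v 20, 19 v 21 and 18 v 22, Wald coverage is still below 95% at 97 to 98 of 100 ordered rate pairs, with lowest values of 83.7% to 85.1%. Conflicts with the coded test fall to 2 of 420, 10 of 440 and 12 of 437 tables.

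**Mortality.** If neither arm has a death, both terms under the root are zero and the Wald interval has zero width.

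**The case against.** The strongest reply is that this matters little. The interval belongs to a sensitivity analysis, the primary inference is the logistic model, and the study is unpowered proof-of-concept. SAP 6.12.4 treats supportive analyses as descriptive. The code already contains a sound test, exact limits and Barnard's test. The conflicts are thin: in all 14 tables the coded p-value lies between 0.053 and 0.058, and the Wald limit clears zero by only 0.3 to 1.1 points. They also become fewer when the arms are unequal, and the SAP says only approximately 40. Finally, the recommended methods also fall below 95% in 29 and 23 of the 55 pairs.

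Most of this stands, and it sets the weight at minor. It does not remove the point. The prose names Wald alone, so the exact output has no stated role. The coverage shortfall, unlike the conflict count, persists with unequal arms. The fair comparison is the size of the shortfall: Miettinen-Nurminen and Newcombe never fall below 93.6% and 94.0% on this grid, while Wald is below 94% in 46 of 55 pairs.

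A reader might go further and infer that the primary logistic model is also defective. It puts several terms on about 40 binary outcomes ("This model will include treatment as a factor, and study site, remdesivir use (No/Yes), dexamethasone use (No/Yes) and WHO Ordinal Scale"), and its prose gives no rule for separation, whereas the repeated-measures model has a fallback ("If this model does not converge then the following covariance matrices will be used in order until the model converges"). The documents do not support that conclusion. The example code announced for the logistic model is absent from the extracted text, so a penalised or exact option cannot be ruled out. Any estimate of how often separation would occur needs site numbers, covariate mixes and response rates that the documents do not give.

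**Conclusion.** The point holds as a minor error in the plan as written. At 20 per arm, with true rates assumed between 50% and 95%, the specified 95% interval has median coverage of 93.5% and is usually 1 to 3 points short. The 85.8% figure is an extreme corner and should not be read as typical. The disagreement with the coded test is real but borderline, and its frequency depends on the arm sizes.

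Two further inferences would go too far. The responder-rate p-value is not invalid, because the coded null-variance test holds its level closely (at most 5.3% on the rates checked). Nor is the Phase 3 decision shown to be compromised, because the protocol summary attaches no interval or p-value rule to it. What changes is how certain the difference looks.

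**What to change.** In SAP 6.12.1, replace the Wald limits with Miettinen-Nurminen (cl=mn) or Newcombe limits, for both the primary endpoint and mortality. Miettinen-Nurminen is the closer fit to the existing code, since at 20 v 20 it agrees with the null-variance test in all 441 tables. State in the text that the null-variance p-value is the reported test, and that the exact limits and Barnard's test are supportive.

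The cost is one SAS keyword and a sentence. At true rates of 90% v 70%, the interval would exclude zero in 35.7% of trials with Miettinen-Nurminen or 34.2% with Newcombe, instead of 40.5% with Wald. The coded test already rejects in only 35.7%, so Miettinen-Nurminen gives up nothing against it. Newcombe is conservative when both rates are very high (99.8% coverage at 95% v 95%).
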